Appendix J: Modifications to the clinical investigation plan

Change from Post Surveillance Registry (PSR) CIP V4.0 to Reveal LINQ Registry CIP V1.0		
Applicable Sections	Change	Rationale
Section 2.2	
Study Description: The study is expected to be conducted at approximately 100 study sites globally with approximately 2,300 subjects contributing to total enrollment numbers.
 
Participating geographies are expected to include, but are not limited to: the United States, Europe Middle East and Africa (EMEA), China and Japan.
	Description of sites, subjects and geographies within the Reveal LINQ Registry
Section 6.1	
Primary Objective:
 
V.4: Characterize clinical actions initiated by Reveal LINQ AF detection.
 
V.1: Characterize clinical actions initiated by Reveal LINQ arrhythmia detection.
	To support reporting on clinical actions initiated by Reveal LINQ for all arrhythmias detected
Section 6.3	
Inclusion criteria:
 
 • Subject or legally authorized representative provides written authorization and/or consent per institution and geographical requirements • Subject is intended to have a Reveal LINQ ICM inserted in the next 30 days • Subject consent prior to Reveal LINQ ICM insertion 	Specific to Reveal LINQ product and consent prior to insertion for data collection and reporting

Section 7.3	Site activation: Additional document collection requirements added	Business requirement
Section 7.9	Follow-up: 
 Changed from required at minimum every 12 months to every 6 months post-insertion. Added: Medtronic requests that the site send any copies of imaging testing results completed as part of standard of care by the time the subject is exited from the study Added section for Arrhythmia Event and Action Taken Assessment (ongoing)	More frequent and robust data collection/reporting
Section 9	Adverse Events: Device deficiency collection added	Added safety collection
Change from Reveal LINQ Registry CIP V1.0 to V2.0		
Applicable Sections	Change	Rationale
Table 6	System-related description	List of options errant

The purpose of the Reveal LINQ Registry is to generate reliable long-term “real world” data of product performance, economic valuation, site-of-service procedural information, and will assist with identification of the Reveal LINQ Insertable Cardiac Monitor (ICM) in the care pathway. The primary endpoint will characterize clinical actions initiated by Reveal LINQ arrhythmia detection and estimate procedure-related acute infection rate.

The registry data is intended to benefit and support interests of patients, hospitals, clinicians, regulatory bodies, payers, and industry. Observational data collection in large populations over time provides an effective means of assessing product performance, patient safety and other clinical outcomes.

This post market registry is not required by any regulatory body. However, data collected in this registry may be submitted to a regulatory body for specific purposes when appropriate.

The study is expected to be conducted at approximately 100 study sites globally. Participating geographies are expected to include, but are not limited to: the United States, Europe Middle East and Africa (EMEA), and Japan. Subjects will be followed for 3 years or until study closure.

All subjects will be followed in-office in accordance with standard care practices of their respective care provider. In the version of the protocol associated with this document, follow-up data collection is required at minimum every 6 months post-insertion (previously 12 month follow-up intervals were required) and real time reporting is required for arrhythmia events and actions taken as a result of the Reveal LINQ ICM. This data may be collected via in-office subject clinic visit, remote monitor transmissions review, or chart review. Subjects are followed until subject death or exit, the implanted device becomes inactive or explanted, the subject has been followed for 3 years, or study closure.

The purpose of the Statistical Analysis Plan (SAP) is to describe the minimal requirements for statistical methods that will be used to analyze study objectives stated in the CIP.

4. Study Objectives

Primary Objectives:

- Characterize clinical actions initiated by Reveal LINQ arrhythmia detection
- Estimate procedure-related acute infection rate

Ancillary Objectives:

A large rectangular area of the page is completely blacked out, indicating that the content for Ancillary Objectives has been redacted.

5. Investigation Plan

The Reveal LINQ Registry will characterize clinical actions and procedure related data in subjects implanted with Medtronic Reveal LINQ ICM.

The study is observational in nature.

Patients will be screened to ensure they meet all of the inclusion and none of the exclusion criteria prior to study enrollment. Ethics Committee approval of the Reveal LINQ Registry Clinical Investigation Plan and Informed Consent Form or Data Release Form must be obtained prior to enrolling patients in the study.

Subjects are considered enrolled in the study upon signing the Informed Consent Form or Data Release Form. In the version of the protocol associated with this document, enrollment of the subject must occur before insertion of the Reveal LINQ ICM. In previous versions of the protocol, subjects were allowed to enroll post-consent.

Inclusion criteria

- Subject or legally authorized representative provides written authorization and/or consent per institution and geographical requirements
- Subject is intended to have a Reveal LINQ ICM inserted in the next 30 days

- Subject consent prior to Reveal LINQ ICM insertion

Exclusion criteria

[figure not shown]
- Subject who is, or is expected to be inaccessible for follow-up
- Subject with exclusion criteria required by local law
- Subject is enrolled in a concurrent study that may confound the results of this study. Co-enrollment in any concurrent clinical study (including registries) requires approval of the study manager or designee.

6. Statistical Methods

6.1. Study Subjects

6.1.1. Disposition of Subjects

Subject flow will be summarized using STROBE guidelines as follows:

6.1.2. Clinical Investigation Plan (CIP) Deviations

Deviations from the CIP will be summarized by type.

6.1.3. Analysis Sets

A set of analysis datasets will be created based on forms (enrolled, procedure, follow-up (including deaths & exits), atrial fibrillation (AF) ablation, events, deviations). A flagging variable will indicate whether or not subject was enrolled prior to LINQ product insertion procedure.

Only subjects enrolled prior to LINQ insertion will be used in safety analyses of procedure-related adverse events and will comprise the Safety Analysis Set. For all other analyses, any study subjects may be used, comprising the Full Analysis Set.

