9. ADVERSE EVENTS AND DEVICE DEFICIENCIES

Reporting and analysis of safety data are mandated by regulatory authorities worldwide. Medtronic has established procedures in conformity with worldwide regulatory requirements to ensure appropriate reporting of safety information. This study is conducted in accordance with these procedures and regulations.

Since the safety reporting requirements and classification systems vary for each regulatory agency, requirements from all geographies are taken into account for the collection and reporting of safety information.

The Reveal LINQ ICM is approved with demonstrated evidence of safety and effectiveness for their intended use. It is not the purpose of the study to demonstrate product safety and effectiveness for the purpose of obtaining product approval nor to obtain approvals for expanded indications of use, new material or design change for medical device already on the market.

For the Reveal LINQ registry, all AEs occurring after consent that are potentially system related or procedure related will be collected, as well as:

- Stroke
- Transient ischemic attack (TIA)
- Bleeding events, and
- Ablation-related events
 - Espophageal injury, phrenic nerve injury, PV stenosis/occlusion, silent microembolism, late hematoma, pseudoaneurysm, AV fistula, dry cough, hemoptysis, other

In all geographies, Unavoidable AEs, listed in Table 5 need not to be reported if resolved within the timeframe specified.

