9.1 Adverse Event Assessment

9.1.1 Adverse Events

AE definitions are provided in Table 5. AEs that are potentially system related or procedure related as well as stroke, TIA, bleeding events, and ablation-related events will be collected and reported to Medtronic during the study, starting from the time the subject completes consent. Reporting of these events to Medtronic will occur on the AE eCRF.

Each AE must be recorded on a separate AE eCRF and include a description of the event, the diagnosis, the date of event onset, the date the site became aware of the event, the relatedness and seriousness of the event, diagnostic tests and procedures performed, actions taken as a result of the event, and the outcome of the event. Documented pre-existing conditions are not considered AEs unless the nature or severity of the condition has worsened. Additionally, detected arrhythmias (including AF) for which no intervention is made are not reportable as AEs. In all geographies, Unavoidable AEs, listed in Table 5 need not to be reported if resolved within the timeframe specified.

For AEs that require immediate reporting (see Table 7), initial reporting may be done by phone, or on the CRF completing as much information as possible. The AE CRF must be completed as soon as possible.

In case the investigator requires information from the sponsor in an emergency situation, the investigator can contact the study sponsor (Table 1).

An assessment for Device Related, Procedure-Related Events as well as stroke, TIA, bleeding events, and ablation-related events will be conducted at each subject follow-up. Submit any

additional supporting evidence which could assist in the assessment and review of reported events e.g. device transmissions and/or device uploads.

9.1.2 *Device Deficiencies*

Device deficiency information will be collected throughout the study and reported to Medtronic. Device deficiencies that did not lead to an Adverse Event should be reported as a device deficiency only.

9.1.3 *Processing Updates and Resolution*

For any changes in status of a previously reported AE (i.e. change in actions taken, change in outcome, change in relatedness), an update to the original AE must be completed. All reported AEs must be followed until the AE has been resolved, is unresolved with no further actions planned, the subject exits the study or until study closure, whichever occurs first.

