9.2 Adverse Event and Device Deficiency Definitions

All reportable AEs and device deficiencies will be reviewed by a Medtronic representative. AEs will be classified according to the definitions provided.

Where the definition indicates “device”, it refers to any device used in the study. Refer to Appendix I for event definitions. Every effort has been made to align study definitions with the ISO 14155:2011 standard but since the study is not within the scope of ISO, minor modifications have been made to better align with the purpose of the study. Specifically, the reference to the term “investigational” has been removed from the definitions with all other content unchanged.

Table 5: Adverse Event Definitions

General	
Adverse Event (AE) (ISO 14155-2011, 3.2)	
Any untoward medical occurrence, unintended disease or injury, or untoward clinical signs (including abnormal laboratory findings) in subjects, users or other person, whether or not related to the medical device
 
Note 1: This definition includes events related to the medical device or the comparator
 
Note 2: This definition includes events related to the procedure involved
 
Note 3: For users or other persons, this definition is restricted to the medical device.

Adverse Device Effect (ADE) (ISO 14155:2011, 3.1)	
Adverse event related to the use of a medical device.
 
Note 1: This definition includes any adverse event resulting from insufficient or inadequate instructions for use or the deployment, implantation, installation, or operation, or any malfunction of the medical device.
 
Note 2: This definition includes any event resulting from user error or from intentional misuse of the medical device

Device Deficiency (DD) (ISO 14155:2011, 3.15)	
Inadequacy of a medical device with respect to its identity, quality, durability, reliability, safety or performance.
 
NOTE: Device deficiencies include malfunctions, use errors and inadequate labeling

Relatedness	
Procedure Related	An adverse event that occurs that is directly related to the implantation or modification of the Reveal LINQ system.
System Related	An adverse event that results from the presence or performance (intended or otherwise) of any component of the system (including: Reveal LINQ ICM, Programmer, Patient Assistant, and MyCareLink Patient Monitor).
Seriousness	

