6.4. Handling of Missing Data and Dropouts

Missing data imputation methods will not be used for the study objectives unless specified otherwise within the analysis methods.

As reflected in specific analysis methods below, any analyses related to infections could be biased by the fact that in prior versions of the protocol, subjects were allowed to be enrolled up to 30 days post insertion. Subjects who had an early infection (especially if it lead to an early explant) may have been less likely to have enrolled post-procedure. Thus, subjects enrolled after day of insertion will not be included in analyses of procedure-related adverse events.

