6.10. Safety Evaluation

Adverse events will be summarized by relatedness (procedure & component (ICM, insertion tool, incision tool, other)), seriousness, and event primary diagnosis.

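### Adverse events not classed as procedure-related may be summarised with subjects enrolled up to 30 days after insertion, so early counts or rates in SAP 6.10 could be understated

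*SAP*

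**What the plan says.** SAP 6.1.3 defines two sets. The first is restricted: "Only subjects enrolled prior to LINQ insertion will be used in safety analyses of procedure-related adverse events and will comprise the Safety Analysis Set". The second takes the rest: "For all other analyses, any study subjects may be used, comprising the Full Analysis Set". A flag variable records whether each subject enrolled before the insertion procedure.

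SAP 6.4 explains the restriction. Under earlier protocol versions, "subjects were allowed to be enrolled up to 30 days post insertion". It then gives the selection argument for infection: "Subjects who had an early infection (especially if it lead to an early explant) may have been less likely to have enrolled post-procedure". The exclusion that follows is again confined to procedure-related events.

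Protocol section 9 sets the collection rule: "all AEs occurring after consent that are potentially system related or procedure related will be collected", with stroke, TIA, bleeding and ablation-related events listed alongside. Section 9.1.1 repeats that reporting runs "starting from the time the subject completes consent".

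Protocol Table 5 defines system-related separately from procedure-related: "An adverse event that results from the presence or performance (intended or otherwise) of any component of the system".

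SAP 6.10 is one sentence. It begins "Adverse events will be summarized by relatedness" and adds the component involved (ICM, insertion tool, incision tool, other), seriousness and diagnosis. It names no analysis set, denominator, time origin or rule for late entry.

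**The concern.** The protection against late enrolment depends on how an event is classified. An event marked procedure-related is analysed only in subjects observed from insertion. An early event marked system-related only, or a stroke, TIA or bleed, falls to the set that may also hold late enrollees. Such a subject counts in the denominator from insertion, but under the current rule an event before consent would not be collected.

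The selection argument in SAP 6.4 is not specific to infection. A subject whose device was explanted early for another reason would also have been less likely to enrol afterwards. Both mechanisms push early figures downward.

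The SAP already accepts the reporting gap elsewhere. For Primary Objective #1 it adds a sensitivity analysis that allows for follow-up time, because late enrollees may have under-reported actions between insertion and consent. The visible text has no counterpart for these adverse events.

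What is at stake is the early part of the descriptive safety tables in a registry meant to describe product performance. Component-level rows for insertion and incision tools are the clearest case. Harm from a tool arises at insertion, and it is protected only if it is also marked procedure-related.

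**Working it through.** The plan gives no figure to reproduce here, so the check sets the rules side by side and then scales the possible loss.

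**Chain of rules**

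1. Events not procedure-related go by default to the Full Analysis Set (SAP 6.1.3).
2. That set can include subjects enrolled up to 30 days after insertion (SAP 6.4).
3. Adverse events are collected from consent (protocol 9 and 9.1.1, current version).
4. No late-entry rule applies to the summary (SAP 6.10).

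**Formula.** Let *f* be the share of the set enrolled after insertion, and *s* the share of their events, within the period summarised, that fall before consent. A crude rate with everyone in the denominator is the true rate × (1 − *f* × *s*), so the relative understatement is *f* × *s*. Selection is left out and would add to it. The documents give neither *f* nor *s*; the values below are assumptions.

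**Constant hazard over full follow-up.** Follow-up is 1096 days (protocol 7.9.5) and the longest delay to consent is 30 days, so *s* is at most 30/1096 = 2.7%.

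- *f* = 20%: 0.20 × 30/1096 = 0.5%
- *f* = 60%: 0.60 × 30/1096 = 1.6%

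Earlier consent makes these smaller. Shorter follow-up makes them larger: at half the follow-up (548 days) they double to about 1.1% and 3.3%. This is relevant because SAP 6.2 and 6.8 foresee analyses while the study is running.

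**Events concentrated near insertion.** With a larger *s*:

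| Share of events before consent (*s*) | *f* = 20% | *f* = 60% |
|---|---|---|
| 2.7% (constant hazard, 30-day delay) | 0.5% | 1.6% |
| 25% | 5% | 15% |
| 50% | 10% | 30% |

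The lower two rows need events clustered soon after insertion, or a table confined to that period, together with late consent. The documents show neither the timing of such events nor the delays.

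**Primary objectives.** Objective #2 requires enrolment before implant (SAP 6.9), so its infection rate is outside this gap. Objective #1 concerns diagnoses and actions, not adverse events, and has its own follow-up-time sensitivity analysis.

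**The case against.** The case for leaving the SAP alone has several parts.

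- **The set wording is permissive.** SAP 6.1.3 allows any subject to be used but does not require it, and SAP 6.10 names no rate. This stands: the bias follows from the default reading and would arise only in a crude early count or rate over the Full Analysis Set.
- **The collection rule is the current one.** Late enrollees came in under earlier versions that are not available. A reader might infer that their early events could not be recorded at all. The documents do not show that. For Objective #1 the SAP speaks only of possibly incomplete reporting. That the same rule applied earlier is an inference.
- **Many early events are already protected.** A pocket problem attributable to the insertion is procedure-related by definition, and Protocol Table 6 does not make the two kinds of relatedness exclusive. This narrows the gap to early events not marked procedure-related.
- **Most listed events are long-term.** Stroke, TIA and bleeding are followed for up to 3 years, and ablation-related events concern procedures that mostly come after consent. For these the loss is small, and restricting every table to pre-insertion enrollees would discard valid data. This also stands and shapes the fix.
- **Redaction.** The ancillary analyses are blacked out, so handling of late enrollees there cannot be ruled out.

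None of this supplies a denominator or time origin for SAP 6.10.

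**Conclusion.** The point holds in a limited form. As written, the SAP lets early adverse events that are not procedure-related be summarised over subjects who may not have been observed from insertion. Counts or rates for about the first 30 days could be too low. The direction is downward whenever some subjects enrolled late and some of their events fell before consent. This rests on the current consent rule having applied to them and on a crude summary being used.

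The size cannot be determined. For long-term events it is about 0.5 to 1.6% relative, assuming a constant hazard, full 3-year follow-up and 20 to 60% enrolled late.

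A reader might infer a loss of 5 to 30%. That needs 25 to 50% of the late enrollees' events to precede consent, which nothing in the documents supports for events over the whole follow-up. A reader might also infer that a key safety result of the registry is biased. The visible objectives do not include a system-related event rate, and neither primary objective is affected. This is a worthwhile, inexpensive improvement to a descriptive table.

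**What to change.** Amend SAP 6.1.3 and 6.10 as follows.

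- Report adverse events of any relatedness in the first 30 days after insertion in the Safety Analysis Set only. This removes the uncollected time and avoids the selective late enrolment described in SAP 6.4.
- For later events keep the Full Analysis Set, but count person-time from consent (delayed entry), so that no subject contributes time before being observed. Delayed entry alone does not remove selective enrolment, so show the same results in pre-insertion enrollees as a sensitivity analysis.
- State the denominator and time origin of each SAP 6.10 table.

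The flag needed already exists, so no new data are required. The price is a smaller denominator, and hence less precision, in the early table, plus slightly more analysis work. Long-term events keep the full sample.

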6.2. General Methodology

Medtronic employees or designees will perform all statistical analyses. Additional exploratory analyses of the data may be conducted as deemed appropriate. Data analysis may be carried out throughout the study without having all enrolled subjects completing study required follow-ups.

6.3. Center Pooling

Centers/investigators will be pooled for analysis of study objectives.

6.4. Handling of Missing Data and Dropouts

Missing data imputation methods will not be used for the study objectives unless specified otherwise within the analysis methods.

As reflected in specific analysis methods below, any analyses related to infections could be biased by the fact that in prior versions of the protocol, subjects were allowed to be enrolled up to 30 days post insertion. Subjects who had an early infection (especially if it lead to an early explant) may have been less likely to have enrolled post-procedure. Thus, subjects enrolled after day of insertion will not be included in analyses of procedure-related adverse events.

6.5. Adjustments for Multiple Comparisons

No adjustments are planned for multiple comparisons.

6.6. Demographic and Other Baseline Characteristics

Baseline characteristics and relevant medical history will be collected on eCRFs for all enrolled subjects. Baseline characteristics will be summarized for all enrolled subjects. Baseline variables to be summarized may include, but are not limited to: age, sex, race, height, weight, LVEF, NYHA, medical history (symptoms), cardiovascular surgical/intervention history, general cardiovascular history, spontaneous arrhythmia history, diagnostic/monitoring history and baseline medications,

For continuous variables, mean, standard deviation, median, and range will be reported. For categorical variables, frequency and percentage will be reported.

